1. INTRODUCTION

The purpose of this reporting and analysis plan (RAP) is to describe the analyses to be included in the Clinical Study Report for protocol

GlaxoSmithKline Protocol Number	Date	Version
2015N252007_00	2016-MAY-26	Original
2015N252007_01	2016-SEP-16	Amendment No. 1
The purpose of this amendment is to support country-specific requirements for South Korea including an update to inclusion criteria age for local regulatory requirements and the addition of study investigational product labels within Appendix 8.		
2015N252007_02	2016-NOV-02	Amendment No. 2
The purpose of this amendment is to support country-specific requirements for Sweden based on local regulatory requirements and to provide additional protocol details and clarifications requested by the MPA.		
2015N252007_03	2016-DEC-13	Amendment No. 3
The reasons for this amendment were to: update medical monitor/SAE contact information; provide additional clarity for assessments to be conducted during the Extension Phase; add text to instruct contact of the Medical Monitor upon the occurrence of rash during the CAB + RPV oral lead-in period; specify a secondary lipid objective and endpoint within the study objectives; provide clarity around dosing at the Day 1 visit; allow serum pregnancy testing instead of urine testing in the event that urine testing is not available; provide clarification that cabotegravir and rilpivirine exposure may persist for more than one year following IM injections, emphasize that participants should continue to use HAART for at least one year following the last CAB + RPV injection, and that female participants of childbearing potential must continue to use adequate contraception for at least one year after the last CAB + RPV injection; expand the allowance of short treatment courses of topical, inhaled, or intranasal glucocorticoids to 21 days or less; add additional guidance for the definition of a change in ART regimen for inclusion/exclusion criteria; provide additional guidance on when to contact the Medical Monitor upon a serofast RPR result for screening syphilis test; clarify language within exclusion criteria #9; added text regarding the treatment assignment randomization schedule; remove a requirement to record within the eCRF how frequently IP was taken on average and the requirement to record any treatment delays or dose reductions of IP; add text to indicate that drugs known to cause Torsade des Pointes (TdP) should be used with caution with rilpivirine; remove limits on the duration for use of topical imiquimod; add clarity around reflexive testing for HBV DNA for participants with positive anti HBc and negative HBsAg and negative anti-HBs results; add temperature collection as part of vital signs to the Time and Events table; add requirement that all sites should have a plan in place for managing possible risks for suicide related events; clarify text regarding PK sample		


window collection; clarify text for patient reported outcome endpoints and timings for completion of questionnaires relative to other clinical assessments and procedures, add clarification for prohibited medication information; remove information in the Appendix requiring collection of pregnancy information for female partners of male study participants; incorporate updates from country-specific amendments No 1, and No 2. into a global protocol amendment; add text that additional details of the injection device used by sites for IM administration including, but not limited to functional performance, may also be collected within the eCRF; clarify that commercial availability of CAB LA + RPV LA includes availability through local public/government health sectors; add allowance that in exceptional circumstances, local labs can be reviewed and approved by the Medical Monitor for consideration of participant eligibility; add information that Screening HLA-B*5701 result is not required to inform eligibility status; add other minor corrections and edits to protocol text.
		
2015N252007_04	2017-NOV-02	Amendment No. 4

The reason for amendment 4 is to acknowledge the potential rollover of eligible 201585 (ATLAS) study participants following the Week 52 visit and completion of time point for the primary analysis to the 207966 (ATLAS-2M) study examining the efficacy, safety and tolerability of CAB LA + RPV LA administered every 4 weeks (Q4W) compared to CAB LA + RPV LA administered every 8 weeks (Q8W). Specifications for the procedural rollover of 201585 participants are included within amendment #4. Due to the planned transition of eligible participants to ATLAS-2M following the time point completing Week 48 primary analysis, the snapshot virologic response at Week 96 and in the Extension Phase for ATLAS is no longer valid and has been replaced with the proportion of participants with plasma HIV-1 RNA < 50 c/mL over time including Week 96. Exploratory analyses evaluating the effect of patient characteristics on virologic and immunologic responses in the treatment arms are also limited to a Week 48 analysis. The reporting timeline of pregnancy event and follow-up pregnancy form has been updated from 2 weeks to 24 hrs of identification of a pregnancy event, and within 24 hrs of investigator awareness of pregnancy outcome, respectively. Updated references for the cabotegravir and rilpivirine investigator brochures have been added.
		

2. SUMMARY OF KEY PROTOCOL INFORMATION

2.1. Changes to the Protocol Defined Statistical Analysis Plan

There were no changes or deviations to the originally planned statistical analysis specified in the protocol / protocol amendment #4 [(Dated: 02/NOV/2017)].

OR

Changes from the originally planned statistical analysis specified in the protocol are outlined in [Table 1](#).

Table 1 Changes to Protocol Defined Analysis Plan

Protocol	Reporting & Analysis Plan	
Statistical Analysis Plan	Statistical Analysis Plan	Rationale for Changes
No change	No change	

2.2. Study Objective(s) and Endpoint(s)

Objectives	Endpoints
Primary Objectives	Primary Endpoints
To demonstrate the non-inferior antiviral activity of switching to intramuscular CAB LA + RPV LA every 4 weeks (monthly) compared to continuation of current first line antiretroviral regimen over 48 weeks in HIV-1 infected antiretroviral therapy (ART)-experienced participants	
 Proportion of participants with a 'virologic failure' endpoint as per Food and Drug Administration (FDA) Snapshot algorithm at Week 48 (Intent-to-Treat Exposed [ITT-E] population).
Secondary Objectives	Secondary Endpoints
To demonstrate the antiviral and immunologic activity of switching to intramuscular CAB LA + RPV LA every 4 weeks (monthly) compared to continuation of current ART	
 Proportion of participants with Plasma HIV-1 RNA <50 copies/mL (c/mL) at Week 48 using the FDA Snapshot algorithm (Missing, Switch or Discontinuation = Failure, Intent-to-Treat Exposed [ITT-E] population). Proportion of participants with plasma HIV-1 RNA <200 c/mL at Week 48 using the Snapshot algorithm (ITT-E population) Proportion of participants with confirmed virologic failure (two consecutive plasma HIV-1 RNA levels \geq200 c/mL after prior suppression to <200 c/mL) through Week 48 Absolute values and change from Baseline in plasma HIV-1 RNA (\log_{10} c/mL) at Week 48. Absolute values and change from Baseline in CD4+ lymphocyte count at Week 48 Incidence of disease progression (HIV-associated conditions, acquired immunodeficiency syndrome [AIDS] and death over 48 Weeks
To evaluate the safety and tolerability of switching to CAB LA + RPV LA every 4 weeks (monthly) compared to continuation of current ART	
 Incidence and severity of adverse events (AEs) and laboratory abnormalities over time including Week 48 Proportion of participants who discontinue treatment due to AEs over time including Week 48 Absolute values and changes in laboratory parameters over time including Week 48
To evaluate the effects of CAB LA + RPV LA every 4 weeks on fasting lipids over time compared to continuation of	
 Change from Baseline in fasting lipids over time including Week 48 and Week 96.

Objectives	Endpoints
current ART over time.	
To assess viral resistance in participants experiencing confirmed virologic failure (CVF)	
 Incidence of treatment emergent genotypic and phenotypic resistance to CAB, RPV and other on-study ART through Week 48
To assess the impact of Baseline third agent treatment class (INI, NNRTI, or PI) on efficacy, safety, tolerability, and viral resistance of CAB LA + RPV LA compared to continuation of current ART	
By Baseline third agent treatment class:
 
 Proportion of participants with a 'virologic failure' endpoint as per FDA Snapshot algorithm at Week 48 (Intent-to-Treat Exposed [ITT-E] population). Proportion of participants with Plasma HIV-1 RNA <50 c/mL at Week 48 using the FDA Snapshot algorithm (Intent-to-Treat Exposed [ITT-E] population) Incidence and severity of select AEs and laboratory abnormalities over time including Week 48 Proportion of participants who discontinue treatment due to AEs over time including Week 48 Absolute values and changes in select laboratory parameters over time including Week 48 Incidence of observed genotypic and phenotypic resistance to current antiretroviral regimen and to CAB or RPV for participants meeting confirmed virologic failure (CVF)
To characterize CAB and RPV concentrations and population pharmacokinetics and identify important determinants of variability.	
 Plasma PK parameters for CAB LA and RPV LA (when evaluable, C_{trough}, concentrations post dose [$\sim C_{max}$], and area under the curve [AUC]) Demographic parameters including, but not limited to, age, sex, race, body weight, body mass index, and relevant laboratory parameters will be evaluated as potential predictors of inter- and intra-participant variability for pharmacokinetic parameters

To evaluate the antiviral and immunologic effects, safety, tolerability, and viral resistance of CAB LA + RPV LA for participants during the Extension Phase
 
 For participants randomized to CAB LA+ RPV LA at Day 1 For participants electing to 	
 Proportion of participants with plasma HIV-1 RNA < 50 c/mL over time including Week 96 (observed case) Proportion of participants with confirmed virologic failure (two consecutive plasma HIV-1 RNA levels ≥ 200 c/mL after prior suppression to <200 c/mL)

Objectives	Endpoints

transition to CAB LA + RPV LA in the Extension Phase
	
through Week 96
 
 • Absolute values and change from Baseline in plasma HIV-1 RNA over time including Week 96 • Absolute values and changes from Baseline in CD4+ cell counts over time including Week 96 • Incidence of disease progression (HIV-associated conditions, acquired immunodeficiency syndrome [AIDS] and death) • Incidence and severity of AEs and laboratory abnormalities over time including Week 96 • Proportion of participants who discontinue treatment due to AEs over time including Week 96 • Absolute values and changes in laboratory parameters over time including Week 96 • Incidence of treatment emergent genotypic and phenotypic resistance to CAB, RPV, and other on study ART through Week 96

To assess the acceptance of pain and injection site reactions following injections
	
 • Change from Week 5 in Dimension scores (“Bother of ISRs”, “Leg movement”, “Sleep”, and “Injection Acceptance”) and individual item scores assessing pain during injection, anxiety before and after injection, willingness to be injected in the future and overall satisfaction with mode of administration over time using the Perception of iNjection questionnaire (PIN) • Proportion of participants considering pain and local reactions following injection to be extremely or very acceptable based on the acceptability score over time using the Perception of iNjection questionnaire (PIN)

To assess degree of health-related quality of life (HRQoL)
	
 • Change from Baseline in HR QoL using the HIV/AIDS-targeted quality of life questionnaire (HAT QoL) short form at Week 24, Week 48, Week 96 (or Withdrawal).

To assess the health status
	
 • Change from Baseline in health status at Week 24, Week 48, and Week 96 (or Withdrawal) using the 12-item Short Form Survey (SF-12).

To assess treatment satisfaction of CAB LA + RPV LA compared to
	
 • Change from baseline in total “treatment satisfaction” score, and individual items scores of the HIVTSQs at

Objectives	Endpoints
continuation of current ART	Weeks 4b, 24, 44, 96 (or Withdrawal) 
 Change in treatment satisfaction over time using the HIVTSQc at Week 48 (or Withdrawal)
To assess treatment acceptance	
 Change from Baseline in treatment acceptance at Week 8, Week 24, Week 48, Week 96 (or Withdrawal) using the “General acceptance” dimension of the Chronic Treatment Acceptance (ACCEPT) questionnaire
To assess tolerability of injections	
 Change from Week 4b in tolerability of injection at Week 5, Week 40, Week 41, and Week 96 using the Numeric Rating Scale (NRS) within the CAB + RPV LA arm.
Exploratory Objectives	Exploratory Endpoints
To explore the effect of patient characteristics (e.g., demographic factors, Baseline CD4+) on the virologic and immunologic responses to CAB LA+ RPV LA compared to continuation of current ART	
 Proportion of participants by patient subgroup(s) (e.g., by age, gender, BMI, race, HIV-1 subtype, Baseline CD4+) with Virologic Failure over time including Week 48 using the Snapshot algorithm for the ITT-E population Proportion of participants by patient subgroup(s) (e.g., by age, gender, body mass index (BMI), race, HIV-1 subtype, Baseline CD4+) with plasma HIV-1 RNA <50 c/mL over time including Week 48 using the Snapshot algorithm for the ITT-E population Change from Baseline in CD4+ cell counts by subgroups at Week 48
To explore relationship(s) between plasma concentrations of CAB and RPV and pharmacodynamic endpoints.	
 Relationship between plasma PK concentrations and virologic, immunologic responses, and/or occurrence of adverse events [AEs] over time may be explored.
To evaluate renal and bone biomarkers in participants treated with CAB LA + RPV LA compared to continuation of current ART	
 Absolute value and change from Baseline in renal (in urine and blood), and bone (in blood) over time
To assess preference for CAB LA+ RPV LA compared to oral ARV using a single dichotomous preference question.	
 For patients randomized to the “CAB LA + RPV LA” arm, preference for CAB LA + RPV LA compared to oral ARV regimen, at Week 48 For patients randomized to the “Current ART” arm who switched to the injectable treatment, preference for CAB LA + RPV LA compared to current ART regimen at Week 96 (end of extension phase-secondary analysis)
To assess reason for switching using a single question.	
 The reasons for willingness to switch ART at baseline for both treatment arms and for patients randomized to the “Current ART” arm at Week 52.

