- n. An overnight fast is preferred; however, a minimum of a 6-hour fast is acceptable.
- o. Only collect if the Withdrawal visit occurs at Week 48, or 96.
- p. Blood sample for renal and bone biomarker assessments: **Renal:** Cystatin C; Retinol Binding Protein (RBP); **Bone:** bone specific alkaline phosphatase, procollagen type 1-N-propeptide, type 1 collagen cross-linked C-telopeptide, osteocalcin, 25 hydroxy-Vitamin D
- q. Whole blood/PBMC collection samples may be used for virologic analyses. PBMCs will be collected at Day 1, Week 96, and Withdrawal if prior to Week 96.
- r. Informed consent for genetic research must be obtained before sample collection
- s. One blood sample for CAB and RPV each to be collected at each PK timepoint. PK samples are to be collected pre-dose during visits requiring IM administration. 2-hour post dose samples also taken at Weeks 4b, 48, 56b, and 96. Pre-dose samples at Weeks 56b, 60, and 2 hour post-dose sample at Week 56b are only for subjects transitioning from Current Art arm to CAB LA + RPB LA. Pre-dose samples are to be collected after review of PK diary at Week 4b and 56b and prior to the final oral dose of CAB + RPV. Additionally, PK samples will be taken during the 1-week post-dose Week 5 and 41 visits. PK window allowed for sample collection; includes 3 to 10 days for 1-week post dose sample (Visits 5 and 41); ±one hour for 2-hour post dose sample (Weeks 4b, 48, 56b, and 96).
- t. Only for Participants entering CAB LA+ RPV LA Oral Treatment
- u. Participants switching to CAB LA + RPV LA will take final dose of oral lead-in regimen in the clinic at The Week 4b visit or Week 56b and begin injections. If possible, injections should be spaced approximately 2 cm from one another and from the site of any previous injection and or any injection site reaction. Bring RPV LA to approximately room temperature prior to injecting. Time and location of injection (right or left) as well as needle length used will be collected in the eCRF. The first injection can be performed as soon as central lab results become available and safety parameters are reviewed.
- v. With the exception of the NRS, all Patient Report Questionnaires/Surveys are recommended to be administered at the beginning of the visit before any other assessments are conducted and prior to administration of the NRS is to be given post injection. Conduct questionnaires/surveys at Withdrawal if occurring prior to Week 96.

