- w. HIV TSQ (c) to be administered at Week 48 to LA injection arm only
- x. "Reason for switch" will be administered prior to randomization at Day 1. At Week 52, "Reason for Switch" will be given only to participants randomized to the "Current ART" arm.
- y. Preference" question to be administered at Week 48 to patients randomized to CAB LA + RPV LA arm, and at Week 96 to patients randomized to the "current ART arm" who switched to CAB LA + RPV LA at the end of maintenance phase.
- z. NRS will be administered on injection visits approximately 30-60 minutes following injections. Participant should record the maximum level of pain experienced with the most recent injections.

Note: BP – Blood pressure, HR – Heart Rate, HDL – High Density Lipoprotein, LDL – Low Density Lipoprotein, PT Prothrombin Time, PTT Partial Thromboplastin Time, INR International normalized ratio

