13.3.4. Assessment Window for Health Outcome Data

13.3.4.1. NRS

NRS questionnaire assessments are assigned to analysis visits based on the windows defined in [Table 13](#).

Table 13 Assessment Windows for Maintenance Phase NRS Questionnaire Data

Domain	Parameter	Target Date	Analysis Window	Analysis Timepoint
NRS	All	Date of 1 st Injection	Assessment Date \leq Date of 1 st injection + 2	Week 4
		Date of 1 st injection+7	Date of 1 st injection + 3 \leq Assessment Date \leq Date of 1 st injection + 42	Week 5
		Date of W40 Injection	If participant received Week 40 injection: Date of WK40 injection - 42 \leq Assessment Date \leq Date of W40 Injection + 2	Week 40
		Date of 1 st Injection + 252	If participant did not receive Week 40 injection: Date of 1 st injection + 210 \leq Assessment Date \leq Date of 1 st injection + 280	

Domain	Parameter	Target Date	Analysis Window	Analysis Timepoint
		Date of W40 Injection + 7	If participant received Week 40 injection: Date of W40 Injection + 3 ≤ Assessment Date ≤ Date of W40 Injection + 28	Week 41
		Date of 1 st Injection + 308	If participant received Week 40 injection: Date of 1 st Injection + 280 < Assessment Date ≤ Date of 1 st Injection + 350 AND Assessment Date > Date of WK40 injection + 28	Week 48
		Date of 1 st Injection + 308	If participant did not receive Week 40 injection: Date of 1 st Injection + 280 < Assessment Date ≤ Date of 1 st Injection + 350	

Note: Apply NRS analysis windows only to assessments that are on-treatment (per [Table 20](#)) within the Maintenance phase (Per [Table 17](#))

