13.3.4.3. Evaluable Criteria for Observed Case Displays – PIN and NRS only

Post the visit slotting as described above, data that is assessed outside of 5-9 days post injection at Week 5/41 for NRS/PIN, and data at Week 4b/40 for NRS that is not assessed on the same day as CAB+RPV injections are received will be excluded from Observed Case Displays (see Table 14). However, these data will still be used for LOCF Displays.

Table 15 Evaluable Criteria using Time Window for non-LOCF summaries

Endpoints	WK4B	WK5	Wk40	WK41
PIN (Q4W)		X (within Day 5-9 post injection)		X (within Day 5-9 post injection)
NRS (Q4W)	X (on the same day of WK4B injection)	X (within Day 5-9 post injection)	X (on the same day of WK4B injection)	X (within Day 5-9 post injection)

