7.25.	ITT-E	Shell THO2	Proportion of Subjects with HIV-Treatment Satisfaction Questionnaire Individual Item Scores change) (Maintenance phase)		WK48
7.26.	ITT-E	Shell THO1	Summary of HIV-Treatment Satisfaction Questionnaire in Treatment Satisfaction Score Change)(Maintenance phase)		WK48
7.27.	ITT-E	Shell THO5	Statistical Analysis of HIV-Treatment Satisfaction Questionnaire in Treatment Satisfaction Score Change at Week 48 ())(Maintenance phase)	ANOVA for analysis	WK48

Health Outcomes : Tables					
No.	Population	IDSL / TST ID / Example Shell	Title	Programming Notes	Deliverable
Treatment Acceptance (ACCEPT)					
7.28.	ITT-E	Shell THO2	Proportion of Subjects with Treatment Acceptance Questionnaire(ACCEPT) Individual Item Scores by Visit - LOCF)(Maintenance phase)		WK48
7.29.	ITT-E	Shell THO1	Summary of Acceptance/General Dimension Score (ACCEPT Questionnaire) by Visit (Maintenance phase)		WK48
7.30.	ITT-E	Shell THO1	Summary of Acceptance/General Dimension Score (ACCEPT Questionnaire) by Visit - LOCF(Maintenance phase)		WK48
7.31.	ITT-E	Shell THO1	Summary of Change from Baseline in Acceptance/General Dimension Score (ACCEPT Questionnaire) by Visit (Maintenance phase)		WK48
7.32.	ITT-E	Shell THO1	Summary of Change from Baseline in Acceptance/General Dimension Score (ACCEPT Questionnaire) by Visit - LOCF(Maintenance phase)		WK48
7.33.	ITT-E	Shell THO3	Statistical Analysis of Change from Baseline in Acceptance/General Dimension Score (ACCEPT Questionnaire) by Visit – LOCF (Maintenance phase)	ANCOVA for analysis	WK48
Tolerability of Injection, NRS (for Q4W IM)					
7.34.	ITT-E	Shell THO2	Proportion of Subjects with Tolerability of Injection (NRS) Individual item scores by Visit - LOCF)(Maintenance phase)		WK48
7.35.	ITT-E	Shell THO9	Summary of Tolerability of Injection(NRS) scores by Visit (Maintenance phase)		WK48
7.36.	ITT-E	Shell THO9	Summary of Tolerability of Injection(NRS) scores by Visit - LOCF) (Maintenance phase)		WK48
7.37.	ITT-E	Shell THO9	Summary of Tolerability of Injection (NRS) by Visit - Change from Week 4B Scores)(Maintenance phase)		WK48

Health Outcomes : Tables					
No.	Population	IDSL / TST ID / Example Shell	Title	Programming Notes	Deliverable
7.38.	ITT-E	Shell THO9	Summary of Tolerability of Injection (NRS) by Visit - Change from Week 4B Scores - LOCF)(Maintenance phase)		WK48
Preferences (Dichotomous preference question)					
7.39.	ITT-E	Shell THO8	Treatment Preference at Week 48 (Maintenance phase)		W48
Willingness to switch					

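### NRS ratings made about a week after injection (Weeks 5 and 41) are expressed as change only from a same-day rating (Week 4b), so those changes are not like for like; the Week 40 cell of Table 15 is also wrong

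*SAP*

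**What the plan says.** Section 2.2 gives one endpoint for the objective on tolerability of injections, within the CAB + RPV LA arm: "Change from Week 4b in tolerability of injection at Week 5, Week 40, Week 41, and Week 96 using the Numeric Rating Scale (NRS"). Table 7.37 (Section 13.13.9) carries it out as "Summary of Tolerability of Injection (NRS) by Visit - Change from Week 4B Scores", and Table 7.38 repeats it with LOCF. Both use Week 4b as the reference for every visit.

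The ratings are of two kinds.

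- **Same day (Weeks 4b and 40).** Footnote z of the Schedule of Events (Section 13.2.1) states that "NRS will be administered on injection visits approximately 30-60 minutes following injections", and that "Participant should record the maximum level of pain experienced with the most recent injections". Section 13.3.4.3 excludes from observed-case displays "data at Week 4b/40 for NRS that is not assessed on the same day as CAB+RPV injections are received".
- **About one week later (Weeks 5 and 41).** Footnote s describes these as one-week post-dose visits: "PK samples will be taken during the 1-week post-dose Week 5 and 41 visits". Section 13.3.4.3 excludes "data that is assessed outside of 5-9 days post injection at Week 5/41 for NRS/PIN". Table 13 sets the Week 41 target at "Date of W40 Injection + 7".

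Table 15 restates the evaluability rule cell by cell. Its Week 40 NRS cell requires assessment on the day of the Week 4b injection.

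**The concern.** A change score measures change over time only if both ratings are made in the same way. Here one reference, given within an hour of the first injection, serves visits rated within an hour and visits rated after about a week. If the participant rates the worst pain since the most recent injection, the later rating covers the first hour and everything after it.

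At stake is the reading of the only endpoint listed for this secondary objective. In a by-visit table, Weeks 5 and 41 could sit above Week 40 because of when the question was asked, and the Week 41 figure could be taken as loss of tolerability, or as less improvement than occurred.

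The Table 15 cell has its own consequence. Programmed as written, it would remove every Week 40 score from the observed-case displays, leaving Table 7.37 with only the two changes that are not like for like.

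**Working it through.** The SAP states no sample size, power or expected value for the NRS, so there is no figure to reproduce. The check is one of structure, followed by an illustration on assumed inputs.

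**1. Which injection, and how long after it**

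| Visit | Injection rated | Time since injection |
|---|---|---|
| Week 4b | first | about 30-60 minutes |
| Week 5 | first | 5-9 days |
| Week 40 | Week 40 | about 30-60 minutes |
| Week 41 | Week 40 | 5-9 days |

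**2. What each planned change contains**

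- Week 40 - Week 4b: different injections, same timing. Like for like.
- Week 5 - Week 4b: same injection, different timing. If the rating is the maximum since injection, the longer period contains the shorter, so apart from recall error the difference is zero or positive. It holds no information on change over time.
- Week 41 - Week 4b = (Week 41 - Week 5) + (Week 5 - Week 4b): the like-for-like change plus the timing term.

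**3. Illustration**

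All inputs are assumptions: 0-10 scale; mean first-hour pain 3; mean later peak 1, 3 or 5; a shared participant effect with SD 1.2; within-injection SD 1.0 (immediate) and 1.5 (later); scores rounded and kept within 0-10; one-week rating = the larger of immediate and later pain; true improvement of 0, 1 or 2 points by Week 40 in both components; 200,000 simulated participants.

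| Later peak | True improvement | W5-W4b | W40-W4b | W41-W4b | W41-W5 |
|---|---|---|---|---|---|
| 1 | 0 | 0.12 | 0.00 | 0.12 | 0.00 |
| 1 | 1 | 0.12 | -0.94 | -0.84 | -0.95 |
| 1 | 2 | 0.12 | -1.78 | -1.70 | -1.81 |
| 3 | 0 | 0.71 | 0.00 | 0.71 | 0.00 |
| 3 | 1 | 0.71 | -0.95 | -0.28 | -0.98 |
| 3 | 2 | 0.71 | -1.78 | -1.20 | -1.90 |
| 5 | 0 | 2.10 | 0.00 | 2.10 | 0.00 |
| 5 | 1 | 2.10 | -0.94 | 1.11 | -0.99 |
| 5 | 2 | 2.11 | -1.78 | 0.13 | -1.97 |

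The smallest individual W5-W4b value was 0 throughout, as step 2 requires. W41-W4b follows the true improvement but is shifted upward by the timing term. W41-W5 and W40-W4b recover the improvement closely, apart from a small loss because scores cannot fall below 0.

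A closed form gives the equal-mean case. For bivariate normal immediate and later pain with equal means and SDs and correlation rho, the expected excess of the maximum is SD x sqrt((1 - rho)/pi): 0.47, 0.40, 0.31 and 0.18 SD for rho = 0.3, 0.5, 0.7 and 0.9. At an assumed SD of 2 points this is about 0.94, 0.80, 0.62 and 0.36 points. The table shows that the gap between mean immediate and mean later pain matters more than the correlation.

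**4. LOCF**

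Section 13.7.2.2 carries forward the previous non-missing on-treatment value. In visit order, a missing Week 40 score (same day) would be filled from Week 5 (one week), and a missing Week 41 score from Week 40. Section 13.3.4.3 also keeps out-of-window values in LOCF displays. So in Table 7.38 even Week 40 against Week 4b may mix the two kinds of rating.

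**5. Table 15 against its own text**

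The prose of Section 13.3.4.3 ties the Week 4b and Week 40 ratings to the day injections are received. Table 15 ties the Week 40 rating to the Week 4b injection. Week 40 falls 36 weeks after Week 4b, and 36 x 7 = 252 days, the offset Table 13 itself uses for Week 40. No Week 40 score can meet the cell as written.

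**The case against.** **The one-week recall is inferred.** No recall length is stated for Weeks 5 and 41, footnote z gives clock timing only for injection visits, and the NRS text in Section 13.6.6 is withheld for copyright. This stands. The claim that Week 5 can only equal or exceed Week 4b depends on the maximum-since-injection reading. The narrower point does not: ratings made within an hour and after 5-9 days are not interchangeable, whatever the direction of the difference. The withheld section might also hold an NRS-specific imputation rule; the LOCF remark rests on the general one.

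**A reader might infer that the Week 41 change reflects recall length and not tolerability.** The documents do not support that. Week 41 against Week 4b contains the real change and moves with it (+0.71, -0.28, -1.20 for improvements of 0, 1 and 2 points at later peak 3). Only Week 5 carries no information on change over time.

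**A reader might also conclude that an improvement would be masked, or attach a size such as 0.6-0.9 points.** Neither follows. If later pain is low, a true 1-point improvement still shows as -0.84. The 0.6-0.9 range needs equal mean immediate and later pain, an SD of 2 and a correlation of 0.3 to 0.7, none of which the SAP gives.

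**Other displays limit the harm.** Tables 7.34-7.36 show NRS scores by visit, so Week 41 can be read beside Week 5. The PIN is reported as change from Week 5 and includes pain during injection, and injection site reactions are summarised by visit and maximum severity. Table 7 plans no NRS test. All of this stands and sets the severity.

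**The Table 15 prose makes the intent clear.** It does, but Table 15 is the form a programmer is likely to code from, and the two should agree.

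**Conclusion.** The concern holds in limited form. Week 5 minus Week 4b is a within-injection contrast, not a change in tolerability over time. Week 41 minus Week 4b confounds elapsed or recall time with real change, and could understate or reverse an improvement if later pain exceeds immediate pain. The size cannot be fixed from the SAP: under the assumed inputs the timing term runs from about 0.1 to 2.1 points. Its direction rests on the maximum-since-injection reading of footnote z.

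Week 40 against Week 4b is sound in observed-case data, provided Table 15 is not applied literally. The Table 15 error is independent of any assumption about recall.

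Severity is minor: a descriptive, single-arm secondary endpoint with no test and no bearing on the primary or key secondary comparisons.

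**What to change.** - In Tables 7.37 and 7.38, add Week 41 change from Week 5 as the over-time comparison for one-week ratings. The data are already collected, and the PIN already uses Week 5 as its reference.
- Keep the defined Week 4b endpoint. Weeks 40 and 96 stay against Week 4b as the over-time comparison for injection-day ratings (Week 96 when that analysis is reported). Label Week 5 and Week 41 against Week 4b as immediate versus one-week contrasts.
- In the LOCF displays, do not carry values between same-day and one-week ratings: fill Week 40 only from an earlier same-day score and Week 41 only from Week 5.
- Correct the Week 40 NRS cell of Table 15 to refer to the Week 40 injection.

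The cost is one extra row per table, a short LOCF rule, one corrected cell, and an entry in Table 1 of Section 2.1, which at present records no change from the planned analysis. Participants with no Week 5 score will not contribute to the new row. No new data are needed.
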